5.1. Investigational Device Information

The RHEA Vital Sign Vigilance System is designed for continuous and contact-less measurement of heart rate and respiratory rate. The system will also notify users when the patient exits the bed. The system is intended for continuous measurement of respiration rate and heart rate for adults ($\leq 150\text{kg}$), in an automatic contact-less manner, in a hospital or clinic setting during sleep or resting condition.

The setup includes placing a sensor under the mattress, and a bedside unit on a nearby flat surface that can be viewed by the investigator.

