5.3. Device Components

The system incorporates the following three components:

- The bedside unit with battery [35 mm(Height) \times 241mm (Width) \times 600mm (Length)]
- The sensor unit [30mm (Height) \times 165mm (Width) \times 261mm (Length)]
- Proprietary exporting data software

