2. Place the Investigational Device sensor unit under the mattress and beneath the chest of the subject. Place the bedside unit on a flat surface or hang on the wall using the bracket.
3. Calibrate the device in accordance with the operator’s manual.
4. Synchronize the date and time of the Investigational Device and Monitor Device (to be equivalent).
5. Place the main units of the Investigational Device and the Monitor in different locations in the subject’s room such that they can only be viewed by their respective testers.
6. After the subject lies down on the bed, place the Monitor Device lead on the subject’s chest in accordance with the operational instruction of the MP/MX series Patient Monitor.
7. Connect the etCO₂ module to the Monitor device and apply the nasal cannula to the subject.
8. Turn on the Monitor Device and the Investigational Device. Set the Monitor Device to “real-time monitoring mode”.
9. Instruct the subject to remain motionless. At one-minute intervals, the two testers will simultaneously record the HR, RR and the current time using their respective device.
10. If HR or RR value does not appear or turns darker and with a mark “?” after the value on the screen (in this state only the last value is displayed rather than the current value), the Investigational Device tester will mark it on the CRF.

11. Stop the test once 20 valid pairs of data are recorded for each subject. If certain values are marked (per Step 10 above), the data at that recorded point will not be considered in the analysis. More than 20 pairs will be collected in order to ensure that there are at least 20 valid pairs.

Motion and Bed Exit Test:

This test will be conducted only on subjects who can move and exit the bed easily.

The Monitor Device tester will ask the subject to turn or move ten times and exit the bed for three times randomly in five minutes. The Monitor Device tester will record the time of these events on the CRF. At the same time, the Investigational Device tester will observe if there is an “unexpected motion” or “bed exit” notification on the screen of the Investigational Device and will record the time of this event on the CRF.

Device Testing Considerations:

1. At the baseline for each subject, make sure the following information is recorded: subject ID, date of birth, gender, height, weight, location, time and clinical diagnosis. Adverse events should be recorded and kept during the tests. The record should be signed by the testers.

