10.1. General Statistics Design

- Investigation site selection: three sites will be selected:
- Randomization: consecutive selection: selecting every subject in the order they present in the site if they meet the inclusion/exclusion criteria till it reach the pre-specified number.
- Blinding: Two investigators observe the results from the investigational device and reference device separately. Time-stamp method (see time synchronization as described in Section 6.3, Testing Procedures) will be used in the comparison.

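### In the motion and bed-exit test, the tester who hand-records RHEA notifications is not masked to the prompts or movements, and the plan does not use the device's own log

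*Combined protocol and SAP*

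**What the plan says.** Section 6.3 gives the motion and bed-exit test to two people. On prompting: "The Monitor Device tester will ask the subject to turn or move ten times and exit the bed for three times randomly in five minutes". On the reference record: "The Monitor Device tester will record the time of these events on the CRF". On the RHEA record: "At the same time, the Investigational Device tester will observe if there is an" on-screen notification of motion or exit; that tester also enters its time on the CRF.

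Two other places bear on masking. In the Investigational Device Accuracy Test, step 5, the main units are put "in different locations in the subject’s room such that they can only be viewed by their respective testers". Section 10.1, under blinding, says: "Two investigators observe the results from the investigational device and reference device separately". Neither refers to the motion test.

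Section 5.1 describes the RHEA set-up as including "a bedside unit on a nearby flat surface that can be viewed by the investigator". Section 5.3 lists "Proprietary exporting data software" among the components, and section 2.1 says the system's data can be exported. No section uses an export for the motion test.

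Section 10.4 treats motion and no-motion accuracy as secondary proportions against manual observation, each with a two-sided 95% confidence interval. It sets no hypothesis or threshold for them.

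**The concern.** For heart and respiratory rate, hiding each screen from the other tester is adequate masking, because the comparator is itself a number on a screen. In the motion test the comparator is a person visibly turning or leaving the bed on request. Hiding a screen does not hide that. A tester who knows an event has just happened knows when to look for a notification, may be readier to accept a late or lingering one as belonging to that event, and may be less ready to write one down when nothing has happened.

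This test is the plan's only clinical evidence on motion and exit detection. Bed-exit notification is part of the intended use in sections 2.1 and 5.1, and section 3 makes detection of motion and exit the purpose of the third test. The HR and RR results cannot corroborate it, and a larger sample would not remove a systematic recording error.

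**Working it through.** **The plan's own figures.** The plan gives no figure for motion or bed-exit accuracy. Its sample size (10.6) concerns the primary RMSD endpoints only. A one-sample t test with difference 3.25 − 3.0 = 0.25, SD 0.75 and two-sided alpha 0.05 needs N = 73 (power 80.2%), and 73/0.95 = 76.8, so 77 enrolled. Both figures reproduce, and neither depends on this point.

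**Is the RHEA tester masked?** Taking the texts in turn:

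1. Section 6.3, step 5, separates displays. It is written for the accuracy test and is not repeated for the motion test. Even if it carries over, it does not screen the subject.
2. Section 10.1 separates readers of RHEA and EarlySense. Under section 3 those devices monitor the subject in separate periods, and EarlySense has no part in the motion test.
3. The motion-test text has no step that hides prompts or movements from the RHEA tester.
4. That the tester is in the room is an inference. Section 5.1 puts the bedside unit nearby, and step 5 puts both main units in the subject's room. The motion-test text does not say so outright.

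**Where can an error enter?** The device issues the notification and the tester copies it. An error needs a notification that is missed, wrongly entered, mistimed or matched to the wrong event. Ten motions plus three exits in 300 s is 300/13 = 23 s per event on average, so a late notification can fall close to the next event. Section 10.4 gives no matching window.

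**Illustration of size (assumed values, not from the documents).** Let p be the true detection rate and f the share of missed motions wrongly credited. Then recorded accuracy = p + f(1 − p). The comparison column is 1.96 × √(o(1 − o)/730), where o is the recorded accuracy and 730 = 73 × 10 motions. That is the maximum for 73 completers, since only subjects who can move easily take the test. It ignores clustering within subject, so real intervals would be wider.

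| p | f | Recorded | Shift (points) | Naive 95% half-width (points) |
|---|---|---|---|---|
| 0.80 | 0.10 | 0.820 | +2.0 | 2.79 |
| 0.90 | 0.10 | 0.910 | +1.0 | 2.08 |
| 0.95 | 0.10 | 0.955 | +0.5 | 1.50 |
| 0.80 | 0.25 | 0.850 | +5.0 | 2.59 |
| 0.90 | 0.25 | 0.925 | +2.5 | 1.91 |
| 0.95 | 0.25 | 0.9625 | +1.25 | 1.38 |

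At f = 0.10 the shift lies within the half-width in all three cases. At f = 0.25 it exceeds it in two of three. No matching calculation is possible for no-motion accuracy, because 10.4 does not define what counts as one occurrence of no motion.

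**The case against.** The strongest reply is that the tester only transcribes. The device produces the notification, no rating is asked for, and two people keep separate time records. This largely stands. It limits the risk to recording, timing and matching, but does not remove it, because the hand record is the only RHEA record the motion test calls for.

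Second, if the step 5 layout carries over, the person keeping the manual reference cannot see the RHEA screen. That is real protection, but it protects the reference log and not the RHEA log.

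Third, the direction is not settled. With an event every 23 s on average, a tester who glances at the subject could miss a notification, which would lower recorded detection. This stands: a bias in RHEA's favour is plausible, not shown.

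Fourth, part of the late-notification problem comes from the missing matching window and would remain with a fully masked tester. This also stands, and is why the fix includes a window.

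Fifth, the endpoint is secondary and descriptive, and 10.4 gives no separate accuracy measure for bed exit, the function named in the intended use. This limits the weight of the point. It does not argue against an inexpensive improvement.

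**Conclusion.** The plan leaves the RHEA tester unmasked to prompts and movements in the motion and bed-exit test, and neither the screen separation in 6.3 nor the blinding text in 10.1 covers the gap. The consequence is an opportunity for mis-recorded, mistimed or ambiguously matched notifications. It is confined to motion and no-motion accuracy in 10.4. The primary HR and RR analyses and the sample size are untouched.

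A reader might infer that this tester scores the device by judgement and that reported motion accuracy will therefore be inflated. The documents do not support that: the tester records a device-generated message, and nothing in the plan fixes the direction or size of any error. The shifts of 0.5 to 5.0 points tabulated above follow only from the assumed detection and mis-crediting rates.

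The conclusion assumes that both testers are in the subject's room, which is a strong inference from 5.1 and 6.3. On that footing this is a low-cost improvement worth making to a secondary result.

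**What to change.** - **Preferred (6.3 and 10.4).** Take notification type and time from the device's exported time-stamped log, with the hand record as back-up. The documents do not say whether the export holds notifications, so confirm this first. Match notifications to the manual event log with a time window fixed in advance.
- **If the export does not hold notifications.** Have the RHEA tester face the bedside unit with the subject out of view and log every notification, while the Monitor Device tester cues the subject silently from a pre-drawn schedule of event times. Apply the same window. State that sound may leave the mask incomplete, particularly for bed exits.
- **10.1.** Reword the blinding entry to describe the masking actually used, including that for the motion test.

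The cost is protocol wording plus either an export step or a screen and a printed schedule. The same two testers suffice and no subjects are added. The reported accuracy may come out slightly less favourable.

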7.1. Safety Assessments

Included but shall not be limited to the following:

- 1) Electrical shock
- 2) Loose components leading to device failure

- 3) Failure of the device to resume normal operation after power is interrupted

7.2. Stability

Included but shall not be limited to the following:

- 1) Failure in starting the device
- 2) System shuts off unexpectedly during use
- 3) System pauses unexpectedly during use

8. Test Termination and Adverse Event Reporting

The Investigators will complete training before using the devices on any subjects. There is minimal risk of electric shock, overheating, or other mechanical harm from the devices.

8.1. Adverse Device Effects

If an Adverse Event (AE) occurs, the Investigator should terminate the test and take appropriate measures to treat the subject.

The Investigator will report unanticipated adverse device effects and adverse events to the IRB and the Sponsor no later than 10 working days after the Investigator first learns of the effects, and record it in the CRF. The date, time, treatment given, outcome, and relationship to the device in use should be recorded.

If a Serious Adverse Event happens, investigator should terminate the test and take appropriate treatment measures to the subject. The Investigator should also report to the IRB and the Sponsor, and the Sponsor should report to the authority 5 working days after he knows, and will notify the other investigators taking part in this trial.

9.1. Data Handling

The investigators should record the data clearly and correctly in the EDC based on observations on the subjects as collected in the source documents.

The sponsor should monitor whether the test is proceeding as per the protocol and make sure the CRF is reliable, complete and accurate. If omission and mistakes are found, the Investigator will make corrections in the EDC.

9.2. Data Entry and Validation

Data entered in the EDC system will be reviewed by the sponsor. If incomplete or inaccurate data are found a data clarification request will be forwarded to the site for a response. Manual and automated discrepancies will be presented to the site user for resolution or justification. A sponsor representative will review the justification for all unresolvable discrepancies and will close or re-query them. Once all discrepancies and queries have been resolved, the Investigator will review the data and confirm their accuracy with his/her electronic signature in the EDC.

10. Statistical Analysis

10.1. General Statistics Design

- Investigation site selection: three sites will be selected:
- Randomization: consecutive selection: selecting every subject in the order they present in the site if they meet the inclusion/exclusion criteria till it reach the pre-specified number.
- Blinding: Two investigators observe the results from the investigational device and reference device separately. Time-stamp method (see time synchronization as described in Section 6.3, Testing Procedures) will be used in the comparison.

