2.2. Study Objectives

This clinical trial aims to verify that the RHEA Vital Sign Vigilance System can fulfill its intended use and meet its declared performance and functional specifications. Statistical analysis comparing the performance of the RHEA Vital Sign Vigilance System and the reference device EarlySense System 2.0 to the MP/MX series separately aims to demonstrate that the investigational device is substantially equivalent to the cleared reference device-EarlySense System 2.0 in safety and effectiveness.

3. Study Design

This will be a cross-over, ‘self-controlled’ study comparing the investigational device RHEA Vital Sign Vigilance System to an approved under-mattress device, EarlySense System (Model 2.0) (K131379). Both will be compared to the ‘gold standard’ Philips MP/MX series model Patient Monitor. The same Monitor Device must be used across all hospital wards in this study.

The testing will be conducted in three periods. In the Accuracy Tests (periods 1 and 2), one of the contact-free devices will be used to monitor the HR and RR, while being compared with the MP/MX series Patient Monitor. The RHEA investigational device and reference device will be used to monitor the same subject at different times (cross-over design), as the sensors of the two devices are placed at a similar location of the bed. HR and RR will be recorded for all three devices. Comparison of the performance of the two contact-free devices will be performed on the recorded results via statistical analysis. The third test will assess the ability of the RHEA device to accurately detect motion on or exit from the bed, as compared to the manual observation.

Three clinical trial sites will be selected in the U.S. A total of 77 adult subjects will be enrolled to complete 73 subjects (5% drop-out rate anticipated). Please see Section 10 for Sample Size justification. A site may enroll no more than half the total number of subjects for the study; i.e., up to 39 total subjects per site. It is anticipated that 33 days are needed for 77 recruited patients in total.

The testing duration for each subject will be one to two hours, including device placement, measurements, and device removal.

This is a multi-center study to be conducted in three hospitals. Wards in each site should be representative of non-ICU wards in U.S. hospitals (e.g., medical/surgical, oncology, orthopedics, long term acute care).

4. Subject Selection

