6.3. Testing Procedures

The test will be conducted in three parts:

- Reference Device accuracy test
- Investigational Device accuracy test
- Motion and bed exit test

The following terms are used in the testing procedures below:

- Investigational Device (RHEA device)
- Reference Device (EarlySense device)
- Monitor Device (Gold Standard MP/MX series device)

Reference Device Accuracy Test

1. Two testers (Reference Device tester and Monitor Device tester) will record the following subject information in the CRF: subject ID, gender, height, weight, primary clinical diagnosis, time, site location (hospital and ward).
2. Place the Reference Device sensor unit under the mattress and beneath the chest of the subject according to the instructions for use. Place the bedside unit on a flat surface.
3. Synchronize the date and time of the Reference Device and the Monitor Device (to be equivalent).
4. Place the main units of the Reference Device and the Monitor Device in different locations in the subject's room such that they can only be viewed by their respective testers.
5. After the subject lies down on the bed, place the Monitor Device lead on the subject's chest

in accordance with the operational instruction of the Monitor Device.

6. Connect the etCO₂ module to the Monitor Device and apply the nasal cannula to the subject.
7. Turn on the Monitor Device and the Reference Device. Set the Monitor Device to “real-time monitoring mode”.
8. Instruct the subject to remain motionless. At one-minute intervals, the two testers will simultaneously record the heart rate (HR), respiratory rate (RR) and the current time using their respective device.
9. If the HR or RR value does not appear, or turns blurred on the screen (in this state only the last value is displayed rather than the current value), the Reference Device tester will mark it on the CRF.
10. Stop the test once 20 valid pairs of data are recorded for each subject. If certain values are marked (per Step 9 above), the data at that recorded point will not be considered in the analysis. More than 20 pairs will be collected in order to ensure that there are at least 20 valid pairs.

Investigational Device Accuracy Test:

1. Two testers (Investigational Device tester and the Monitor Device tester) will record the following subject information in the CRF: subject ID No., gender, height, weight, primary clinical diagnosis, time, site location (hospital and ward).

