10.2. Primary Variables

The primary variables for the analysis of heart rate (HR) and respiratory rate (RR) are each the overall mean root mean square difference (RMSD), defined as the mean of the individual subject RMSDs. For each subject, the RMSD is calculated as:

$$\text{RMSD} = \text{sqrt}\{ \sum (Y_R - Y_G)^2 / n \}$$

where Y_R and Y_G are the paired values for the RHEA Vital Sign Vigilance System and the gold standard method (Patient Monitor), respectively, and n is the number of data pairs. If motion or a bed exit occurs within 20 seconds preceding the recording period for a given data pair, the data pair at that time point will not be used in the analysis. A total of 20 pairs of measurements are

planned for each subject. If more than 20 measurements are collected for a subject, then only the first 20 will be used. If fewer than 20 measurements are collected for a subject for any reason, that subject will still be included in the analyses.

The primary hypotheses for HR, are as follows:

Adults

$H_0: \mu = 3.25$

vs.

$H_A: \mu < 3.25$,

The primary hypotheses for RR, are as follows:

Adults

$H_0: \mu = 2.25$

vs.

$H_A: \mu < 2.25$,

where μ represents the population mean HR or RR.

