10.4. Secondary Analyses

Accuracy of the RHEA will be compared with that of the Reference Device-EarlySense device. The RMSD for the Reference Device will be calculated for each subject in the same manner as described for the RHEA. Mean accuracy will then be compared between the RHEA and the Reference Device by comparing the individual subject RMSDs by a paired t test at the 5% level of significance.

Bland Altman plots will be presented separately for each subject's raw data, including the limits of agreement, for both the RHEA and the Reference Device methods. In addition, Bland Altman plots will be presented for the set of RMSD estimates across all subjects, along with two-sided

95% confidence intervals for their limits of agreement. Finally, Bland Altman plots of the raw data across all subjects will be presented, along with two-sided 95% confidence intervals for their limits of agreement. Methods discussed in Bland, JM and Altman, DG (4) and (5) will be used to calculate the confidence intervals of the limits of agreement due to the lack of independence of the repeated measurements on the same subject.

Motion and no motion accuracy will each be calculated along with their respective two-sided 95% confidence intervals. Motion accuracy will be calculated as the proportion of times that the device correctly detected motion among all actual occurrences of motion detected manually. Non-motion accuracy will be calculated as the proportion of times that the device correctly did not detect motion among all actual occurrences of no motion detected manually.

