10.5. Subgroup Analyses

Between subject subgroup analyses will include the following subgroups:

- Primary disease
- Type of hospital ward
- Body weight in quartiles
- Study site

Each subgroup analysis will be based on a one-way analysis of variance on the individual RMSDs which includes the subgroup as the factor. Each analysis will be done at a significance level of 0.05.

Within subject subgroup analyses will be performed to compare results under awake and asleep conditions. The RMSD will be calculated for each subject while awake and while asleep. Mean RMSDs will be compared by paired t tests at a significance level of 0.05.

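### The study is called a cross-over but device order is neither randomised nor balanced, so the RHEA versus EarlySense comparison can carry a period effect, in full if the listed order is followed

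*Combined protocol and SAP*

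**What the plan says.** Section 3 states that "The RHEA investigational device and reference device will be used to monitor the same subject at different times (cross-over design"), because the two sensors occupy much the same place in the bed. It defines two accuracy periods but does not say which contact-free device belongs to which period.

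Section 10.1 has a bullet on randomisation: "Randomization: consecutive selection: selecting every subject in the order they present in the site". It describes consecutive enrolment and says nothing about sequence.

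Section 6.3 says "The test will be conducted in three parts" and lists the Reference Device accuracy test, the Investigational Device accuracy test, and the motion and bed exit test. The detailed steps follow the same order. Nothing states that this order is compulsory, and nothing in the text available for review randomises, alternates or balances it.

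Section 10.4 compares the devices by "comparing the individual subject RMSDs by a paired t test at the 5% level of significance", with no term for period or sequence. Section 2.2 gives the aim that the analysis should serve: to show that RHEA is "substantially equivalent to the cleared reference device-EarlySense System 2.0 in safety and effectiveness".

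**The concern.** In a two-period comparison, anything that changes measurement error between the first and second period is added to the device difference unless order is balanced. If every subject has EarlySense first and RHEA second, there is only one sequence, and no later analysis can separate device from period. If sites choose the order, the confounding is partial, uncontrolled and still not modelled.

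The candidates are effects on the size of the error: the subject settling, falling asleep or lying less still, or testers becoming practised. The plan itself treats sleep as a possible influence on RMSD: "Within subject subgroup analyses will be performed to compare results under awake and asleep conditions" (section 10.5). That is a separate test and does not adjust the device comparison.

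The bias can go either way. It can produce a difference between equal devices, or hide a real one. The second matters more where the aim is to support equivalence.

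**Working it through.** **The plan's own figure.** Section 10.6 gives an SD of 0.75, a difference of 0.25 (3.0 against 3.25 for HR, 2.0 against 2.25 for RR) and 80% power. For a one-sample t test at two-sided 5%, the noncentrality at n = 73 is 0.25 × √73 / 0.75 = 2.848 and the power is 0.802. Enrolment is 73 / 0.95 = 76.8, rounded up to 77. Both figures reproduce, but they concern only the primary tests. The plan gives no power for the device comparison.

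**Bias.** Let d be the true RHEA minus EarlySense difference in mean RMSD, p the period 2 minus period 1 shift, and f the share of subjects tested EarlySense first. EarlySense-first subjects have expected difference d + p, and RHEA-first subjects d − p. The unadjusted mean therefore estimates

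d + (2f − 1)p.

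- Listed order for all, f = 1: the bias is p.
- Order left to sites, for example 55 and 18: 2 × 55/73 − 1 = 0.507, so the bias is 0.507p.
- Balanced, 37 and 36: 1/73 = 0.014p unadjusted, and zero with a period term.

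**SD of the paired difference (assumed).** The 0.75 in section 10.6 is for RHEA only. Taking the same SD for EarlySense and a within-subject correlation ρ, SD = 0.75 × √(2(1 − ρ)). This is 1.06 at ρ = 0 and 0.75 at ρ = 0.5.

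**Rejection rate with identical devices (d = 0), n = 73, two-sided 5%.** Fixed-order values come from the noncentral t distribution with noncentrality p√73/SD. The other rows are simulated (40,000 runs).

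| Order and analysis | Shift p | SD 0.75 | SD 1.06 |
|---|---|---|---|
| All EarlySense first, paired t | 0.05 | 8.7% | 6.8% |
| | 0.10 | 20.3% | 12.5% |
| | 0.25 | 80.2% | 51.1% |
| 55/18, paired t | 0.10 | 8.6% | 6.7% |
| | 0.25 | 26.9% | 16.1% |
| 37/36, period term, no carry-over | 0.05 to 0.25 | about 5% | about 5% |

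A higher correlation makes the fixed-order case worse. At ρ = 0.8 (SD 0.474) the rates are 42.8% for 0.10 and 99.3% for 0.25.

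**Masking.** If RHEA were truly worse by 0.25 and the period shift were −0.15, the net expected difference would be 0.10. Detection would fall from 80.2% to 20.3% (SD 0.75) or from 51.1% to 12.5% (SD 1.06).

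**Precision after the fix.** The adjusted estimate is the mean of the two sequence-specific means. At SD 0.75 its standard error is ½ × 0.75 × √(1/37 + 1/36) = 0.08779 on 71 df, against 0.75/√73 = 0.08778 on 72 df. The 95% half-width rises by a factor of 1.0003 and, to three decimals, stays at 0.175 (0.247 at SD 1.06).

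**The case against.** The strongest reply is that each device is read against a simultaneous monitor value, so drift in true heart or respiratory rate largely cancels. Subjects are told to lie still, marked values are dropped, settling times are set, and section 10.2 removes pairs "If motion or a bed exit occurs within 20 seconds preceding the recording period for a given data pair". The session lasts only one to two hours. Tester practice is a weak candidate, since testers are trained, the two devices have separate tester roles, and practice builds up across subjects. All of this stands and narrows the plausible period effect. It does not rule one out, and sleep remains a credible route.

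The size is also assumed throughout: the documents give no period shift, EarlySense SD, correlation or order split. A shift of 0.25 is a third of the RMSD SD and may be too large. The percentages are illustrations, not estimates for this trial.

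The comparison is secondary, and section 2.2 speaks of comparing each device separately with the monitor, so equivalence does not rest on this t test alone. That limits the weight of the point. It is also true that section 10.4 sets no equivalence margin, so a non-significant result would not show equivalence even with balanced order. That is a separate gap, which balancing does not close.

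Finally, balance does most of the work. A plain paired t test under balanced order stays at or below about 5%, but it becomes conservative as the period effect grows. The period term is a refinement with almost no cost.

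**Conclusion.** The concern holds. The plan uses the cross-over label without the feature that protects a cross-over, and its entry on randomisation allocates nothing. If the listed order is followed, the device comparison carries the whole period effect. If order is left to sites, it carries an unknown share, for example about half at 55/18.

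For an assumed shift of 0.10 under the listed order, the 5% test rejects equal devices in about 12.5% to 20% of trials, and for 0.25 in 51% to 80%. This rests on n = 73, equal SDs of 0.75 and a correlation of 0 to 0.5.

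Only the secondary comparison is affected in this way. The primary tests of RHEA RMSD against 3.25 and 2.25, and the sample size, do not use the device contrast. The point should be fixed before enrolment, but it does not invalidate the primary objective.

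**What to change.** - Randomise the order of the two accuracy tests 1:1 within site, in permuted blocks, and record the sequence on the CRF.
- Keep the motion and bed exit test last for everyone. It asks subjects to "turn or move ten times and exit the bed for three times randomly in five minutes" and should never precede an accuracy test.
- In section 10.4, estimate RHEA minus EarlySense as the average of the two sequence-specific mean differences, that is, a paired analysis with a period term.
- Reword the randomisation bullet in section 10.1 so that consecutive enrolment and allocation to sequence are separate items, and state the two sequences in sections 3 and 6.3.

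The cost is a randomisation list, a CRF field and revised wording. Subjects, testers and sample size stay the same, and the loss of precision is negligible. RHEA-first subjects who take the motion test, at most about half, need the RHEA sensor re-placed. The calibration and clock synchronisation in the section 6.3 set-up steps may have to be repeated for them, so a few minutes should be allowed.
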